The study will be conducted at approximately 4 centers within the USA, including hospitals and outpatient psychiatric clinics. A 20% discontinuation rate is anticipated for this SPCD study, thus, a total of 60 subjects will be initially randomized to have at least 48 subjects complete the study. To account for potential screen failures, up to 100 subjects may be consented in order to randomize 60 subjects total.

Subject Eligibility

Inclusion Criteria

Each subject must meet all of the following criteria to be eligible for this study:

1. Males or Females aged 18-65 years inclusive.
2. Primary diagnosis of Schizophrenia established by a structured psychiatric evaluation (SCID) based on Diagnostic and Statistical Manual of Mental Disorders Forth Edition (DSM-IV-TR) criteria.
3. Written informed consent in compliance with 21 CFR part 50 and in accordance with the International Conference on Harmonization (ICH) Good Clinical Practice (GCP) Guidelines.
4. A Positive and Negative Syndrome Scale (PANSS) (Kay et al., 1994) total score ≥ 70 with a score of ≥ 4 on two or more of the following PANSS items: delusions, conceptual disorganization, hallucinatory behavior, suspiciousness, and unusual thought content.
5. A score of ≥ 4 on the Clinical Global Impression—Severity (CGI-S) (Guy, 1976).
6. Confirmation of both diagnosis and severity of psychosis symptoms by an independent MGH SAFER interview.

7. Must have ongoing antipsychotic treatment for at least 8 weeks, with a stable dose for at least 4 weeks. Subjects who have failed to achieve clinically-recognized symptom reduction to at least 1 marketed antipsychotic agent, given at a Physician Desk Reference (PDR)-defined therapeutic dose for \geq 8 weeks during the past 12 months, as assessed by the MGH FAST, will be eligible
8. Understands and is able, willing, and (in the opinion of the investigator) likely to fully comply with the study procedures and restrictions.

Exclusion Criteria

Subjects who meet any of the following criteria will be excluded from the study.

1. Subjects with a history of renal insufficiency, congestive heart failure, cardiac arrhythmias or history of myocardial infarction.
2. Subjects with a history of symptomatic orthostatic hypotension defined as sitting to standing systolic blood pressure \leq 90mmHg or diastolic blood pressure \leq 60mm Hg with any of the following symptoms: lightheaded or dizzy upon standing, blurry vision, weakness, fainting (syncope), confusion, or nausea.

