3. Subjects with any clinically significant abnormalities as determined by medical history, physical exam, clinical and lab evaluation suggestive of an underlying disease state that may, in the opinion of the investigator, confound the results of study, increase risk to the subject, or lead to difficulty complying with the protocol.
4. Subjects on chlorpromazine, PDE-5 inhibitors, nitrites and any medication with CNS effects with the exception of antipsychotic drugs (other than chlorpromazine) anticholinergics, b-adrenergic antagonists, amantadine, biperiden, diphenhydramine, lorazepam, zolpidem, and temazepam.
5. Medications which in the opinion of the PI, and in conjunction with the medical monitor, may be expected to significantly interfere with the metabolism or excretion of sodium nitroprusside, and/or may be associated with a significant drug interaction with sodium nitroprusside that may pose a significant risk to subjects' health and/or confound the study data.
6. Pregnant or breast-feeding patients. Women of childbearing potential must have a negative pregnancy test performed at screening visit prior to randomization and prior to baseline at visits 3 and 6. Women enrolled in this trial must use adequate birth control.
7. Subjects with a current (within the last 3 months) DSM-IV-TR diagnosis of alcohol or substance use disorder or dependence (excluding nicotine) as established by the clinical assessment (SCID) at the screening visit will be excluded.
8. Has tested positive for any of the following: cannabis, opioids, cocaine, amphetamines, barbiturates methadone, methamphetamine and phencyclidine at the screening or baseline visits. If positive, the urine drug toxicology screen may be repeated once based on investigator judgment, but due to safety concerns, the result must be negative for the subject to continue in the study.

9. Subjects at imminent risk of suicide or injury to self or others, as per the opinion of the investigator, or history of significant suicide attempt within the last 6 months as per C-SSRS.
10. Subjects that have taken an investigational drug or taken part in a clinical trial within 30 days prior to screening.
11. Any other reason that, in the opinion of the investigator, would compromise patient safety or integrity of the study

Table 1- Exclusionary Safety Values of Potential Clinical Concern

Hematology	
Leukocytes	<2 or >17.5 x 10 ³ /mm ³
Platelets	<75 or >700 x 10 ³ /mm ³
Comprehensive Metabolic Panel	

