Sodium	<1.1 times the lower limit or >1.1 times upper limit of the reference range
Potassium	<1.1 times the lower limit or >1.1 times upper limit of the reference range
Chloride	<1.1 times the lower limit or >1.1 times upper limit of the reference range
Carbon Dioxide (Bicarbonate)	<1.1 times the lower limit or >1.1 times upper limit of the reference range
Glucose	>2 times the limits of the reference range
Blood Urea Nitrogen (BUN)	>1.3 times upper limit of the reference range
Creatinine	>1.3 times upper limit of the reference range
Calculated Glomerular Filtration	< 60
Total bilirubin	>2 times the upper limit of the reference range
Aspartate amino transferase (AST)	>3 times upper limit of the reference range
Alanine amino transferase (ALT)	>3 times upper limit of the reference range
Alkaline phosphatase (ALP)	>3 times upper limit of the reference range
Creatine phosphokinase (CPK)	>3 times the upper limit of the reference range
Creatine kinase (CK)	>3 times the upper limit of the reference range
Thyroid Stimulating Hormone (TSH)	>1.5 times upper limit of the reference range
Uric acid	>1.5 times upper limit of the reference range
Lipid panel (triglycerides, total cholesterol (C), HDL-C, calculated LDL-C)	>3 times the upper limit of the reference range

Pregnancy

Serum beta human chorionic gonadotropin (Beta- hCG)	< 6 IU/L negative
---	-------------------

Urine Screen for Drugs of Abuse

Per Exclusionary Criteria #6, a subject is excluded from the study if they meet DSM-IV-TR criteria for diagnosis of alcohol or substance use disorder or dependence (excluding nicotine) within the last 3 months as established by the SCID at the Visit 1 (screening). Per exclusionary criterion 8, for all subsequent urine drug screens (performed at Visits 3 and 6) any individual testing positive for a potential drug of abuse without a documented prescription for that medication will be evaluated by the investigator who will determine if the subject should be terminated from the study due to concerns with respect to subject safety and/or confounding of study data.

Rationale for the Inclusion/Exclusion Criteria

Eligibility criteria for this study have been carefully considered to ensure the safety of the study subjects and to ensure that the results of the study are meaningful in support of the research objectives.

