If clinically significant findings, as determined by the PI or medically qualified Sub-Investigator, occur in any vital sign measurement, that measurement should be captured

as an adverse event and will be repeated at medically appropriate intervals until the value returns to an acceptable range, a specific diagnosis is established, or the condition is otherwise explained

Anthropometric Measurements

Weight (kg) (assessed in ordinary indoor clothing with shoes off) will be recorded at the time points indicated in the SOE. Height (cm) will be recorded at Visit 1 (screening) only. Body Mass Index (BMI) will be calculated at all visits in which anthropometrics are collected and is defined as the subject's weight in kilograms divided by the square of the subject's height in meters (kg/m^2). Waist circumference will be measured to the nearest 0.1 cm.

Laboratory Procedures

Laboratory tests will be performed at the site, and each site will provide their laboratory reference ranges to the coordinating center. Screening blood work will be fasting and blood work taken as part of the study treatment monitoring process will be non-fasting as a precautionary measure to reduce the risk of a hypotensive episode.

Routine laboratory panels will include:

Hematology (absolute and percentage): White blood cell (WBC) count with differential (absolute neutrophil count, lymphocytes, monocytes, basophils, and eosinophils), red blood cell (RBC) count, hemoglobin (Hgb), hematocrit (Hct), and platelet count.

Comprehensive Metabolic Panel: glucose, sodium, potassium, calcium, chloride, carbon dioxide, blood urea nitrogen (BUN), creatinine, calculated glomerular filtration rate, uric acid, phosphorus, magnesium, total protein, albumin, lipid panel (triglycerides, total cholesterol, HDL-cholesterol, calculated LDL-cholesterol) aspartate amino transferase (AST), alanine amino transferase (ALT), alkaline phosphatase (ALP), gamma glutamyl transpeptidase (GGT), total bilirubin, creatine phosphokinase (CPK), creatine kinase (CK) thyroid stimulating hormone (TSH) and uric Acid.

Urinalysis: color, appearance, specific gravity, pH, ketones, protein, glucose, nitrite, leukocyte esterase, and occult blood; microscopic examination of sediment will be performed only if the results of the urinalysis evaluation are positive (microscopic examination may include but is not limited to WBC count, red blood cell (RBC) count, casts, and crystals).

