In the event of a SAE, the PI or designate will notify the MGH-CTNI Medical Monitor by phone or email within 24 hours of the event and will email supporting documentation

within 48 hours of the event and then as relevant data is available within the following week.

The PI must inform the IRB immediately regarding any AE (does not have to be causally related) that is both serious and unexpected; or that represents a series of AEs that, on analysis, is unanticipated, or occurs at an unanticipated frequency, or otherwise represents an unanticipated safety risk to the study subject. The IRB may subsequently choose to modify the informed consent or request changes to the protocol.

Treatment-Emergent Adverse Events

A treatment emergent adverse event (TEAE) is an AE that either began following initiation of study treatment or was present prior to the initiation of the treatment, but increased in frequency or severity following initiation treatment, regardless of causality.

All TEAEs (post infusion) will be captured on the subject source documents for all required assessments and data transferred to the eCRF. The reporting PI or medically qualified Sub-Investigator will sign and date the source document and eCRF.

Procedures and follow-up of Subjects Experiencing AEs after Completion of or Withdrawal from the Study

If a subject experiences the onset of a SAE within a period of 30 days following study completion and, in the opinion of the PI or medically qualified Sub-Investigator, it is associated with the study, it will be followed up and reported as described above.

Protocol Waivers and Violations

Protocol Waivers

Protocol waivers will be assessed on a case by case basis by the medical monitor and the principle investigator for this study.

Procedure for Non-Compliant Subjects

Subjects who miss a study visit will be allowed (at the discretion of the PI) to make up that visit the next day. Subjects who miss more than one visit will be discontinued from the study. Subjects who withdraw consent will no longer have data collected for the study. Every effort will be made to maintain contact with patients who are discontinued, but who do not withdraw consent, according to the study schedule for 30 days post-treatment in order to collect safety data.

Protocol Deviation and Violation Definitions

Protocol violations as defined in the table below will be reported as described in the Manual of Operations.

Table 3. Major and Minor Protocol Violations

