	Major Protocol Violation	Minor Protocol Violation
The list of examples is intended as a guide and is not all-inclusive.		
Definition	
A violation that may:
 
Impact subject safety,
 
Affect the integrity of study data, and/or
 
Affect the subject's willingness to participate in the study.
	
A violation that does not:
 
Impact subject safety,
 
Compromise the integrity of study data, and/or
 
Affect the subject's willingness to participate in the study.

Examples (not all-inclusive)	
Failure to obtain informed consent
 
Informed consent obtained by an unauthorized individual
 
Enrollment of a subject who did not meet eligibility criteria for whom a protocol exception was not obtained
 
Performing a study procedure that is not approved by the IRB and/or is not in the protocol
 
Failure to perform a required lab test that, in the opinion of the Site Investigator, may affect subject safety or data integrity
 
Failure to perform or follow a study procedure that, in the opinion of the Site Investigator, may affect subject safety or data integrity
 
Failure to follow safety (AE) management plan
 
Failure to report a SAE to the IRB and/or Coordination Center
	
Implementation of unapproved recruitment procedures
 
Only a photocopy of the signed/ dated consent form is available (the original is missing)
 
Pages are missing from the signed/ dated informed consent form
 
Use of invalid consent form (i.e. without IRB approval or outdated/expired form)
 
Failure to perform or follow an approved study procedure that, in the opinion of the Site Investigator, does not affect subject safety or data integrity
 
Study procedure conducted out of sequence
 
Failure to perform a required lab test
 
Missing lab results
 
Study Visit out of approved window
 
Over-enrollment
 
Enrollment of subjects after IRB approval of the study has expired

		Failure to submit a continuing review application to the IRB before study expiration
Reporting Requirements	Record the date discovered, date occurred, description of event in the Protocol Deviation Log. Notify the Coordinating Center within 24 hours.	Record the date discovered, date occurred, description of event in the Protocol Deviation Log. Notify the Coordinating Center

I. TREATMENT

Dosing

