Treatment unblinding for the study will occur after all clinical data have been received, data inconsistencies have been resolved, and the database is locked, except for safety reasons on a case by case basis (i.e., emergency unblinding).

Interim Analysis

There will be no interim analysis for this trial.

General Statistical Considerations

All collected study data will be presented in subject data listings. Statistical analyses will be performed using SAS® for Windows, version 9.3 or later. Descriptive statistics (n, mean, standard deviation, median, minimum and maximum) will be calculated by treatment group for continuous variables. Frequencies and percentages will be presented by treatment group for categorical variables.

Analysis Populations

The details of the analysis population to be used for the study are described in the below sections. All the subjects who were randomized in the study will be considered for analysis. For the primary and secondary endpoint analyses the following set of subject will be accounted:

- All subjects randomized to the sodium nitroprusside group in Phase 1 of the study (~ 20 subjects)
- All subjects randomized to the Placebo group in Phase 1 of the study (~ 40 subjects)

- All subjects who did not respond to placebo in Phase 1 and were pre-randomized to the sodium nitroprusside group in Phase 2 of the study (~11 subjects)
- All subjects who did not respond to placebo in Phase 1 and were pre-randomized to the placebo group in Phase 2 of the study (~11 subjects)

Intent-to-Treat (ITT) population

The Intent-to-Treat (ITT) population is defined as all randomized subjects. The ITT population will be the primary population for the analysis of the primary, secondary, and additional efficacy endpoints.

Per Protocol (PP) Population

The Per Protocol (PP) population is defined as all randomized subjects who were not associated with a major protocol violation. This population will be identified before the database lock. The PP analysis of primary, secondary and additional endpoints will be considered supportive.

Safety Population

The Safety population is defined as any subject receiving the treatment after randomization. This population will be used for the analysis of safety parameters.

Covariates

For efficacy analyses, baseline values will be used as covariates in the analysis models.

Missing data

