## **Per Protocol (PP) Population**

The Per Protocol (PP) population is defined as all randomized subjects who were not associated with a major protocol violation. This population will be identified before the database lock. The PP analysis of primary, secondary and additional endpoints will be considered supportive.

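### Table 1 sets the low-side exclusion for four electrolytes above the lower normal limit, so normal values are exclusionary as printed

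*Protocol*

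**What the plan says.** Protocol section G follows the numbered exclusion criteria with a table headed "Table 1- Exclusionary Safety Values of Potential Clinical Concern". Its sodium, potassium, chloride and bicarbonate rows carry one identical rule: "<1.1 times the lower limit or >1.1 times upper limit of the reference range". None of the 11 numbered exclusion criteria refers to the table. Criterion 3 covers laboratory findings through the investigator's judgement and gives no numeric limit.

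Four other places bear on the consequences:

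- Section G, Sample Size: "up to 100 subjects may be consented in order to randomize 60 subjects total".
- Section H, Laboratory Procedures: "each site will provide their laboratory reference ranges to the coordinating center". No reference range is printed anywhere.
- Section H, Protocol Waivers: "Protocol waivers will be assessed on a case by case basis by the medical monitor", together with the principal investigator. Table 3 gives as an example of a major violation: "Enrollment of a subject who did not meet eligibility criteria for whom a protocol exception was not obtained".
- SAP, Per Protocol (PP) Population: the set consists of "all randomized subjects who were not associated with a major protocol violation". Protocol section M has the same definition and adds: "The PP analysis of primary, secondary and additional endpoints will be considered supportive".

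**The concern.** The two arms of the rule do not mirror each other. A value above 1.1 times the upper limit is outside the normal range by a margin. A value below 1.1 times the lower limit need not be outside it at all, because that cut-off sits inside the range or, for a narrow range, above its top. The rule therefore bars subjects with normal electrolytes.

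Read literally, the sodium row by itself would stop most otherwise eligible subjects, and the recruitment plan could not be met. If sites read past the wording, about 4 sites have no stated low-side limit to apply in common and must each fall back on investigator judgement under criterion 3. Subjects enrolled against the printed rule without an exception could then be counted as major violators and removed from the PP set, or not, depending on a choice that is not written down.

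**Working it through.** **Inputs.** From the Protocol: the multiplier 1.1 on the lower limit L and the upper limit U (Table 1), and 60 randomized from at most 100 consented (section G, Sample Size). L and U are not in the documents, so every range below is an assumption, in mmol/L. The plan states no figure of its own on this point to reproduce.

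**Step 1, no assumed range needed.** The low-side cut-off is 1.1 × L. For any L > 0, 1.1L − L = 0.1L > 0, so values from L up to 1.1L are normal and exclusionary. This holds for all four analytes at every site.

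**Step 2, share of the normal interval lost.** The share of its width is min(1, 0.1L / (U − L)), which reaches 100% when U/L ≤ 1.1. This is a share of width, not of patients.

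| Analyte | Assumed L–U | U/L | Cut-off 1.1L | 0.1L / (U − L) | Share excluded |
|---|---|---|---|---|---|
| Sodium | 135–145 | 1.074 | 148.5 | 13.5/10 | 100% |
| Sodium | 133–146 | 1.098 | 146.3 | 13.3/13 | 100% |
| Sodium | 134–148 | 1.104 | 147.4 | 13.4/14 | 95.7% |
| Sodium | 132–146 | 1.106 | 145.2 | 13.2/14 | 94.3% |
| Sodium (wide) | 135–150 | 1.111 | 148.5 | 13.5/15 | 90.0% |
| Sodium (wide) | 130–150 | 1.154 | 143.0 | 13.0/20 | 65.0% |
| Chloride | 98–107 | 1.092 | 107.8 | 9.8/9 | 100% |
| Chloride | 96–106 | 1.104 | 105.6 | 9.6/10 | 96.0% |
| Chloride | 95–110 | 1.158 | 104.5 | 9.5/15 | 63.3% |
| Potassium | 3.5–5.0 | 1.429 | 3.85 | 0.35/1.5 | 23.3% |
| Potassium | 3.5–5.2 | 1.486 | 3.85 | 0.35/1.7 | 20.6% |
| Bicarbonate | 21–32 | 1.524 | 23.1 | 2.1/11 | 19.1% |
| Bicarbonate | 22–29 | 1.318 | 24.2 | 2.2/7 | 31.4% |
| Bicarbonate | 24–30 | 1.250 | 26.4 | 2.4/6 | 40.0% |

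With 135–145, for instance, the only sodium values that pass run from 148.5 to 159.5 (1.1 × 145), all of them above normal.

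**Step 3, illustration in subjects.** Assume further that the reference interval is the central 95% of a normal distribution, with mean (L + U)/2 and SD (U − L)/3.92. For 135–145 the mean is 140, the SD is 10/3.92 = 2.551, and z = (148.5 − 140)/2.551 = 3.33, so 0.04% pass the sodium row. The same calculation gives 2.0% (133–146), 3.7% (134–148) and 4.1% (132–146), that is about 0 to 4 of 100 consented. The wide ranges give about 6% (135–150) and 28% (130–150).

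**Step 4, comparison with the plan.** Randomizing 60 of 100 leaves room for (100 − 60)/100 = 40% screen failure from all causes. Every sodium range above implies at least 72% failure (100% − 28%) from this one row.

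**The case against.** The strongest reply is that nobody would apply the rows as printed. No numbered criterion cites Table 1, and the end of its heading sounds like a list of values to look at. The pregnancy entry in the same table prints the passing result, so the table is not a clean list of exclusion triggers. Elsewhere, physicians mark clinical significance only for results outside the normal range, so a normal sodium never comes up for judgement. A rule that almost everyone fails would be noticed at once and queried or waived. The percentages come from ranges chosen by the reviewer. Finally, the PP set is to be fixed before lock, section I requires evaluability decisions to be documented before codes are broken, and the PP analysis is only supportive.

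Much of this limits the consequence. The force of Table 1 is ambiguous, the likely practical effect is a query to the coordinating center, the sodium share does depend on the range, and the PP safeguards already cover part of the request.

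None of it corrects the rows. The pregnancy entry stands under its own heading and is labelled as the negative result; the electrolyte rows carry no such label. Treating the whole table as non-binding would also drop the only numeric renal limits in the documents (urea nitrogen, creatinine, filtration rate), although the safety rationale relies on excluding renal disease. Case-by-case waivers cannot sensibly carry a rule that most normal subjects fail. Even the widest assumed sodium range leaves the pass rate well short of the 60 in 100 needed.

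**Conclusion.** The concern holds. That normal values of four electrolytes are exclusionary as printed follows from the wording alone and needs no assumption. Its size depends on the sites' reference ranges: 94-100% of the normal sodium interval under common assumed ranges, falling to 90% and 65% under unusually wide ones; 63-100% for chloride; about a fifth to two fifths for potassium and bicarbonate. The count of about 0 to 4 passing subjects per 100 (6 to 28 under the wide ranges) rests on the added normality assumption and is illustrative only.

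The error over-excludes; it does not admit subjects with low values. The ITT primary analysis, type I error and power are not touched. What is exposed is uniform eligibility across sites and the membership of the supportive PP set. It should be fixed, but it does not threaten the main result.

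**What to change.** The sponsor and medical monitor should:

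1. Reconcile the low-side wording in the four electrolyte rows so that it does not exclude values within the reference range. The replacement limit is a clinical choice for them, and none is proposed here.
2. State whether Table 1 is a binding exclusion and, if so, cite it from the numbered criteria.
3. Document before database lock, while still blinded, how subjects enrolled under the printed rows are classified for the PP population.

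The cost is an amendment to four table rows with the usual IRB review at about 4 sites, one sentence on the table's status, and a short PP classification rule. No procedure or visit is added.
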